4.6.1 Inclusion criteria

Live newborns with a birth date at least 3months following the launch of the SUNRISE radio campaign will be eligible to be enrolled into the trial.

¹ <https://journals.sagepub.com/doi/10.1177/1536867X1801800204>

4.6.2 Exclusion criteria

Children with major infant congenital defects, children not living with their mother, and children with mothers who are not capable of participating in assessments.

4.6.3 Informed consent

Participants will be approached and recruited from their homes by the trained fieldworkers, who will explain the study by reading an information sheet translated into the local languages of the 15 clusters in the trial. Where a local language does not have a commonly used written format, the information sheet will be written in French and translated orally into the local language by the interviewers, as practised during the training sessions. All translations will be validated using back translation plus pilot testing.

The information sheets include guidance on how information will be kept secure and confidential and the limits of confidentiality during home visits. Participants will be made aware that their decision to participate will not in any way impact their access to existing health services that they may already be accessing. After sharing this information, participants will have the opportunity to ask questions and their understanding will be verified before consent is requested.

If they are happy with the answers they have received and agree to take part, participants will complete a consent form, with their agreement to participate indicated by YES responses to all key aspects of the study followed by a signature on the consent forms, which the fieldworker will also need to sign. Consent will cover recruitment and the 11 follow-up 3-monthly visits. Separate, additional consent processes will be undertaken at the 18-20 month visit in order to obtain consent for video recording of parent-child interactions and at the 30-32 month (final) visit, when mothers will be asked to consent for their child to take part in a developmental assessment.

Signed consent forms will be kept by the mothers; the fieldworkers will take photos of these on their tablets.

4.6.4 Voluntary participation and right to refuse or withdraw

FWs will explain to mothers that their participation in this research is entirely voluntary. They do not have to take part if they do not wish to do so. They may also stop participating at any time they choose. They do not need to explain their reasons for not taking part but it would be helpful if they were able to give us some information about your decision. Whether they choose to participate or not, the mother and her baby will still receive the same care and attention from health centres in their area.

4.7 Schedule of assessments

The trial will be supported by a **surveillance system** with regular 3-monthly visits by the cluster fieldworker (FW) to all households. These visits will be used to recruit the trial participants, maximize their follow-up during the trial and collect a variety of data on ECD behaviours and outcomes as well as process evaluation data on radio listening patterns, according to the schedule shown in Table 3.

Table 3: Schedule of visits and assessments, by age

Visit	1	2	3	4	5	6	7	8	9	10	11
Age (m)	0-2	3-5	6-8	9-11	12-14	15-17	18-20	21-23	24-26	27-29	30-32
Recruitment	X										
Radio Coverage	X	X	X	X	X	X	X	X	X	X	X
ECD Knowledge	X						X				X
ECD Behaviour Assessments											
FCI			X		X		X		X		X
HOME-IT							X				
Observed responsiveness (NICHD)							X				
ECD Outcome Assessments											
CREDI-LF			X		X		X		X		X
CDI			X		X		X		X		X
MDAT (or GSED-LF)											X

Key:	Primary Outcome	X
	Secondary Outcome	X

The assessments include:

- **Radio coverage:** Data will be collected at every 3 monthly visit with questions related to listenership in the past week and child health advice heard on the radio.
- **ECD Knowledge** will be assessed using a subset of questions from the Knowledge of Infant Development Inventory (KIDI, 37) which measures factual knowledge of parental practices, child development processes and norms of behaviour for children 0-3 years of age. It is appropriate for use with persons of limited education and is considered to be culturally neutral. It will be administered at recruitment and again when the child is age 18-29m and 30-32m..
- The **Family Care Indicators** (FCI, 35) survey was developed by UNICEF to assess key caregiving/family home environment variables considered critical for early child development. This has been used very extensively, including in the global MICS surveys. It will be administered 6-monthly starting when the child is age 6-8m.
- The **HOME-IT inventory** (Home Observation for Measurement of the Environment, Infants & Toddler version) provides a comprehensive assessment of the family environment, including the provision and variety of stimulating play materials, the organization of the physical environment, and levels of parental involvement, responsiveness and acceptance of the child's behavior. It will be administered when the child is age 18-20m.

- **Responsiveness** will be directly observed when the child is age 18-20m. Mothers will be video recorded carrying out a set of interactive tasks in which the child is introduced to a series of novel toys; this will last about 15 minutes. The videos will be independently coded, blind to whether the mother is in an intervention or control cluster, using the **National Institute of Child Health and Human Development (NICHD)** sensitivity scales, which assess “a parent’s accuracy in perceiving and interpreting their infant’s cues and their ability to react in a timely and appropriate manner”.
- The long form (LF, 45 items) of the **Caregiver Reported Early Development Index (CREDI, 34)** will be administered 6-monthly starting when the child is age 6-8m. It is a developmental screening instrument designed specifically for large-scale surveys and evaluations for children aged zero to three years. It relies only on parental reporting and assesses 5 domains of early developmental milestones and behaviours, namely Motor, Language, Cognitive, Socio-Emotional and Mental Health, tailored to the child’s age.
- The **Communicative Development Inventories (CDI)** will be administered 6-monthly starting when the child is age 6-8m. It is one of the most widely used and well-validated tools for assessing early language development and is available in many languages. The Words and Gestures short form (Level I) will be used for assessments up to including age 18-20m. This is a parent-reported checklist of early communication and receptive language, comprised of an 89-word vocabulary checklist with separate columns for comprehension and production. The Words and Sentences short form (Level II) of the CDI will be used at later ages. These measures contain a 100-word productive vocabulary checklist and a question about combining words.
- The **Malawi Developmental Assessment Tool (MDAT, 38)** will be administered at the final visit when the child is age 30-32m. This is a well validated in-person developmental assessment conducted by trained fieldworkers, that has been specifically designed and adapted to be appropriate in low resource settings and for a wide range of cultures and contexts. It was based on pre-existing well established developmental assessments, including the Denver Developmental Screening Test and the Griffiths Test, supplemented by new items designed to be relatively culture- and context-free indicators of early child development. It consists of 136 test items, with 34 items covering each of the 4 developmental domains of gross and fine motor development, language and social development. A total norm-referenced z-score can be computed as an overall index of child development. The tool shows excellent inter-rater reliability and good sensitivity and specificity for identifying children with developmental disability/delays. The MDAT has been validated in several sub-Saharan African countries including Burkina Faso.
- The **Global Scales of Early Development – Long Form (GSED-LF)** is a recently devised standardised developmental assessment, drawing on evidence and existing tools (including the MDAT), for use in the programme evaluation of ECD interventions. It consists of 158 test items covering motor, cognitive, language, social, and socio-emotional development. It has been field tested in 6 countries including Cote D’Ivoire. The nature of the assessment and the training requiring is highly similar to the MDAT. Validation of the GSED is being undertaken at the moment and we await the results of those evaluations. During the early phases of this trial, we will evaluate the evidence as it becomes available regarding this possible alternative assessment of child development and consider whether there are advantages to the use of the GSED relative to the MDAT. If a decision is taken to use the GSED-LF this will be ratified by the Trial Steering Committee and notified and approved by the ethics committee via an amendment.

4.8 Trial Outcomes

4.8.1 Primary Outcomes

The primary **impact** outcome, assessed at age 30-32m, will be:

- The total MDAT score measured at the final follow-up visit when children will be aged 30-32 months. Parents in the intervention clusters will have benefited from maximum exposure to the SUNRISE campaign from the third trimester of pregnancy throughout their children's lives.

The primary **intermediate** outcome, assessed when the child is age 18-20m, will be:

- The z-standardized sum score for observed responsiveness from the National Institute of Child Health and Human Development (NICHD) sensitivity scales.

4.8.2 Secondary outcomes

Secondary **impact** outcomes will be:

- The 4 MDAT developmental domain scores for gross and fine motor development, language and social development, assessed at age 30-32m.
- The 5 CREDI-LF scores measured 6-monthly from 6-8 months of age until 30-32 months of age.
- The 5 Communicative Development Inventories (CDI) scores measured 6-monthly from 6-8 months of age until 30-32 months of age.

Secondary **intermediate** outcomes will be:

- The HOME-IT inventory (Home Observation for Measurement of the Environment, Infants & Toddler version) score assessed when the child is age 18-20m.
- The 5 Family Care Indicators (FCI) scores measured 6-monthly starting when the child is 6-8 months of age until they are 30-32 months of age.

4.8.3 Tertiary outcomes

- The two Knowledge of Infant Development Inventory (KIDI) scores measured when the child is 18-20 months of age and when they are 30-32 months of age.

4.9 Cultural adaptation

We will use the following systematic process of cultural adaptation for all instruments:

- a) Translation of the assessment instruments into the 6 local languages spoken by residents in the trial clusters, and adaptation of the testing materials for the local context;
- b) Ensuring technical equivalences;
- c) Cognitive interviews with respondents and project staff (field research);
- d) Modifications of translated versions, based on the field research;
- e) Pretesting, including further modification;

- f) training of assessors, establishing inter-rater reliability; and
- g) Pilot-testing, including testing of standard operating procedures.

4.10 Sample size

We anticipate assessing at least 100 children per cluster, after allowing for a maximum 20% loss to follow-up from recruitment. This will give 90% power to detect an effect size of 0.25, assuming an intra-class correlation of 0.01 (personal communication, from the Save the Children ECD trial in Rwanda) and 80% power to detect an effect size of 0.21. It will also give 90% power to detect an effect size of 0.4 in other ECD outcomes, the level achieved in several successful ECD interventions, assuming an intra-class correlation of 0.04, which is informed by unpublished results from the SPRING trial, and 80% power to detect an effect size of 0.33.

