Fifteen clusters have been identified from across Burkina Faso which satisfy the following conditions: there are at most two dominant radio stations and no discernible broadcast from stations in neighbouring clusters; they are not based in the large cities of Ouagadougou or Bobo-Dioulassou; and they are not subject to any security risk. Eight will be randomised to broadcast the SUNRISE campaign and 7 to act as controls. One hundred and twenty-five babies from each cluster who are born after the campaign has been running for 3 months will be enrolled into the trial and have six-monthly ECD assessments conducted throughout the campaign. All trial procedures will be carried out in full compliance with Good Clinical Practice (GCP) guidelines.

3. The SUNRISE Radio Campaign

The SUNRISE campaign builds on the saturation+ approach successfully used in DMI's previous child survival campaign in Burkina Faso promoting family health behaviour and care seeking for sick children. This approach is based on:

1. Saturation: Broadcasting approximately 10 times per day
2. Science-informed content: Using a variety of evidence-based methods and behaviour change theories to inform campaign design
3. Stories: Using innovative creative techniques within both spots and interactive programming to maximise audience engagement

The SUNRISE campaign will follow DMI's established intervention approach & implementation schedule with:

1. 60-second radio spots, tailored to increase awareness, knowledge, motivation, skills and opportunity regarding the target behaviours. These spots are highly cost-effective as they are short, entertaining and can be repeated multiple times. Over 100 different spots will be produced. We will achieve population saturation of messaging within cluster sites by broadcasting these 60 second spots 10 times every day in each of 6 languages for a week. This weekly cycle will continue for three years. 60-second radio 'spots' broadcast in weekly cycles, 10 times a day, and in 6 languages (i.e. one or two spots plays intensely for a week and then replaced with new spots for the following week and so on). These will include scripted dramas and modelling of responsive parent-child interactions.

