4.6 Trial Participants

The first 125 eligible children born in each cluster after the campaign has been running for three months will be enrolled together with their families. They will be identified through 3-monthly surveillance visits to all compounds identified at baseline; it is expected that recruitment will be achieved within a 6-month period. They will form the **trial cohort** and be followed 3-monthly until the end of the radio campaign. Its impact on ECD nurturing care behaviours and ECD outcomes in the first 3 years of life will be evaluated.

Everyone with access to a radio in the intervention clusters can potentially hear the campaign messages and long programmes. The selection of mothers for the trial cohort to evaluate the impact of the campaign has been specifically chosen to ensure their maximum potential exposure to the SUNRISE radio campaign in the intervention clusters as this will be broadcast during their last trimester of pregnancy until the final ECD outcome assessment of their children.

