4.11 Statistical Methods

Findings will be reported according to the CONSORT guidelines for cluster randomized trials. Analyses will be intention to treat and include all data from trial children and their families, regardless of their exposure to the radio campaign. Random-effects linear regression models using individual-level data will be used to adjust for the clustered design and any imbalances between intervention and control arms. Effect sizes will be presented as standardized mean differences with 95% confidence intervals (CI). The data analysis plan will be published prior to the end of recruitment.

Analyses will initially be carried out blind with clusters randomly allocated randomly to groups X & Y. Results will be presented to the TSC /DMEC and all data procedures and statistical methods agreed. This is in order to ensure that any decisions made concerning methods, choice of indicators, outliers etc cannot be influenced by the trial results. Partially unblinded analyses will then be presented with the two trial groups labelled by letters rather than as intervention and control. The findings will be discussed, and the interpretation of any differences agreed, ignorant to the knowledge of which group is intervention and which control. The code will then be broken. Interpretation of findings cannot be changed at this stage.

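### On the 15-cluster design, the two 80% power figures in section 4.10 come to about 76% and 75% (unadjusted test, 13 degrees of freedom)

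*Protocol*

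**What the plan says.** Section 2 of the protocol fixes the number of clusters: "Eight will be randomised to broadcast the SUNRISE campaign and 7 to act as controls". Section 4.6 sets enrolment: "The first 125 eligible children born in each cluster after the campaign has been running for three months will be enrolled". Section 4.10 converts this to an analysed number, "We anticipate assessing at least 100 children per cluster", "after allowing for a maximum 20% loss to follow-up from recruitment"; that is, 125 × 0.8 = 100.

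Section 4.10 then makes four power statements:

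- at ICC 0.01, 90% for an effect of 0.25 and "80% power to detect an effect size of 0.21";
- at ICC 0.04, for other child development outcomes, 90% for 0.4 and "80% power to detect an effect size of 0.33".

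The section gives no alpha, formula or reference distribution, and no allowance for the number of clusters or for covariates. Section 4.11 plans a random-effects linear model on individual data, adjusted for imbalances between arms, and says "Effect sizes will be presented as standardized mean differences with 95% confidence intervals (CI".

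**The concern.** The campaign is allocated to radio-station areas, so 15 clusters carry the information on the variation against which the arms are compared. A valid 5% test of the arm effect, with equal cluster sizes and no covariates, has 13 degrees of freedom and a critical value of 2.160, not 1.96. That difference costs several points of power. Section 4.4 recognises that there are few clusters when it chooses the randomisation method, but nothing in section 4.10 shows that the power statement does.

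If the stated 80% is too high, the trial runs a 24–25% risk of missing effects of 0.21 or 0.33 where readers are told 20%. A null result would then be read against a sensitivity the design does not have. Section 9.2 also asks the data monitoring committee to keep the sample size assumptions under review, and it needs figures that fit the 8 v 7 design.

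**Working it through.** **Inputs.** Clusters 8 and 7 (section 2); m = 100 assessed per cluster (section 4.10) or 125 enrolled (section 4.6); ICC 0.01 and 0.04 (section 4.10); outcome SD 1, since effects are standardised. Assumed: two-sided alpha 5% (consistent with the 95% intervals of section 4.11), equal cluster sizes, no covariate adjustment.

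**Standard error.** SE = √[ (1 + (m − 1)·ICC)/m × (1/8 + 1/7) ].

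- ICC 0.01, m = 100: design effect 1 + 99 × 0.01 = 1.99; SE = √(0.0199 × 0.26786) = 0.0730.
- ICC 0.04, m = 100: design effect 1 + 99 × 0.04 = 4.96; SE = √(0.0496 × 0.26786) = 0.1153.
- m = 125: SE = 0.0693 and 0.1130.

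**Reproducing the stated figures.** The protocol does not say how they were obtained. Normal critical values for 8 v 7 (power = Φ(d/SE − 1.96)) come close, as do normal values for 7 per arm and a t calculation for 8 v 8 clusters on 14 degrees of freedom, so no single cause can be named.

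**Power on 13 degrees of freedom.** The statistic follows a noncentral t with noncentrality d/SE and critical value 2.160. For 0.21, d/SE = 0.21/0.0730 = 2.88; for 0.33, 0.33/0.1153 = 2.86.

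| Effect (ICC) | Stated | Normal, 8 v 7 | Normal, 7 v 7 | t, 8 v 8 | **t, 8 v 7, m = 100** | t, 8 v 7, m = 125 |
|---|---|---|---|---|---|---|
| 0.25 (0.01) | 90% | 92.8% | 91.2% | 90.9% | **88.5%** | 91.5% |
| 0.21 (0.01) | 80% | 82.0% | 79.5% | 79.1% | **75.8%** | 80.0% |
| 0.40 (0.04) | 90% | 93.5% | 91.9% | 91.6% | **89.3%** | 90.5% |
| 0.33 (0.04) | 80% | 81.7% | 79.2% | 78.7% | **75.4%** | 77.0% |

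**Cross-checks.** A normal formula with one cluster per arm deducted gives 76.3% for 0.21 and 75.9% for 0.33. A simulation of 400,000 cluster-mean t-tests per setting gives 75.7% and 75.4%, with 5.0% rejection under the null. A cut-off of 1.96 applied to a statistic on 13 degrees of freedom has a true two-sided error of 7.2%, so the normal figures of about 82% are not power at the 5% level.

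**Detectable effects, m = 100, 13 degrees of freedom.** ICC 0.01: 0.221 (80%) and 0.256 (90%). ICC 0.04: 0.349 (80%) and 0.405 (90%).

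**Children per cluster for 80% power.** For 0.21: 125.04, so 126. For 0.33: 226.1, so 227, against 125 enrolled. At ICC 0.04 the between-cluster part of the variance dominates, and more children per cluster help little.

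**Sensitivity to the ICC, m = 100.** Power at 0.21 is 80.0% for ICC 0.008 and 71.8% for 0.012. Power at 0.33 is 79.6% for ICC 0.035 and 71.4% for 0.045.

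**The case against.** The strongest reply is that nothing has been miscalculated. With normal critical values the 8 v 7 design meets all four statements, and the unadjusted t-test on 13 degrees of freedom is not a test the protocol names. This stands as to wording: the fault is a missing small-sample allowance. It does not rescue the figures, because the normal cut-off is too lenient for 15 clusters.

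Second, section 4.11 plans adjustment, and section 4.4 balances the arms on four baseline measures. Cutting the variance of the estimated effect by about 10% would restore 80% on 13 degrees of freedom: 1 − (0.21/0.221)² ≈ 0.10 and 1 − (0.33/0.349)² ≈ 0.11. That is plausible, but section 4.10 claims no such gain. Cluster-level covariates also use degrees of freedom: four of them leave 9, and if they explained nothing power would fall to 72.6% and 72.2%.

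Third, 100 per cluster is a floor. Complete follow-up does bring 0.21 to 80.0%, but 0.33 only to 77.0%.

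Fourth, a gap of 4–5 points is no larger than the effect of small changes in ICCs that come from a personal communication and unpublished results, and the 90% statements, which section 4.10 puts first, barely move. This is fair and limits the weight of the point. It is not a reason to print power that the stated inputs do not give.

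**Conclusion.** The concern holds. On the protocol's own cluster numbers, cluster size and ICCs, power is 75.8% for 0.21 and 75.4% for 0.33, which is 4.2 and 4.6 points below the stated 80%. The 90% statements are short by only 1.5 and 0.7 points and are not materially wrong. The 0.33 claim falls short even with every enrolled child assessed; the 0.21 claim is reached only in that case.

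This rests on a two-sided 5% test, equal cluster sizes and no covariate adjustment. A sufficient gain from adjustment could restore 80%, but the protocol neither assumes nor quantifies one. The point should be corrected, but it does not threaten the design. That section 4.11 leaves the reference distribution open is not counted as an error, since that may properly be settled in the analysis plan.

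**What to change.** Rewrite the power statement in section 4.10 for 8 v 7 clusters on 13 degrees of freedom and name the alpha. With 100 assessed children per cluster:

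- ICC 0.01: 80% power for 0.221 and 90% for 0.256 (about 0.22 and 0.26);
- ICC 0.04: 80% power for 0.349 and 90% for 0.405 (about 0.35 and, rounded up, 0.41).

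If the sponsor prefers to keep 0.21 and 0.33 because adjustment is expected to sharpen the comparison, state the size of the gain assumed and the degrees of freedom left. Either way, the test in the analysis plan should be consistent with the calculation.

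The cost is two sentences. The quoted detectable effects become about 0.01–0.02 SD less favourable. Enrolment stays at 125 per cluster and the design does not change.
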